7.2 Participant Discontinuation/Withdrawal from the Study

- A participant may withdraw from the study at any time at his/her own request, or may be withdrawn at any time at the discretion of the investigator for safety, behavioral, or compliance reasons. This is expected to be uncommon.
- The reason for withdrawal should be clearly documented in the source documents and in the CRF: Adverse Event, Lost to Follow-up, Protocol Deviation, or Withdrawal by Participant or Parent / Legally Acceptable Representative.
- The participant will be permanently discontinued both from the study intervention and from the study at that time.
- If the participant withdraws consent for disclosure of future information, the Sponsor may retain and continue to use any data collected before such a withdrawal of consent.
- If a participant withdraws consent, he/she may request destruction of any biological samples taken (unless local law requires not to destroy them), and the investigator must document this in the site study records.
- Withdrawn participants will not be replaced.

Follow-up of Discontinuations

For participants who have prematurely terminated the study, the site should attempt to contact them and complete all scheduled safety follow-ups, except if they specified that they do not want to be contacted again and it is documented in the source document.

For participants where the reason for early termination is lost to follow-up, the site will not attempt to obtain further safety information. See Section 7.3 for definition of "lost to follow-up".

7.3 Lost to Follow-up

A participant will be considered lost to follow-up if he or she repeatedly fails to return for scheduled visits and is unable to be contacted by the study site.

The following actions must be taken if a participant fails to return to the site for a required study visit or cannot be contacted as planned in the SoA:

- The site must attempt to contact the participant and reschedule the missed visit as soon as possible and counsel the participant on the importance of maintaining the assigned visit schedule and ascertain whether or not the participant wishes to and/or should continue in the study.
- Before a participant is deemed lost to follow-up, the investigator or designee must make every effort to regain contact with the participant (where possible, 3 telephone calls and, if necessary, a certified letter to the participant's last known mailing address or local equivalent methods). These contact attempts should be documented in the participant's medical record.
- Should the participant continue to be unreachable, he/she will be considered lost to follow-up.

Discontinuation of specific sites or of the study as a whole are handled as part of Appendix 10.1.

8 Study Assessments and Procedures

- Study procedures and their timing are summarized in the SoA. Protocol waivers or exemptions are not allowed.
- Immediate safety concerns should be discussed with the Sponsor immediately upon occurrence or awareness to determine if the participant should continue or discontinue study intervention.
- Adherence to the study design requirements, including those specified in the SoA, is essential and required for study conduct.
- All screening evaluations must be completed and reviewed to confirm that potential participants meet all eligibility criteria. The investigator will maintain a screening log to record details of all participants screened and to confirm eligibility or record reasons for screening failure, as applicable.

Blood samples will be collected as described in the SoA table (Section 1.2).

The maximum amount of blood collected from each participant over the duration of the study, including any extra assessments that may be required, will not exceed 10 mL for participants 6 months to < 9 years of age or 40 mL for participants \geq 65 years of age. Repeat or unscheduled samples may be taken for safety reasons or for technical issues with the samples.

Guidance and information for the sample collection, preparation, storage, and shipment are provided in the Operating Guidelines.

8.1 Efficacy and Immunogenicity Assessments

8.1.1 Efficacy Assessments

No clinical efficacy data will be obtained in the study.

8.1.2 Immunogenicity Assessments

No immunogenicity data will be obtained in the study.

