1.1 Synopsis

Protocol Title:

Collection of Serum Samples From Children 6 Months to < 9 Years of Age Who Received Fluzone[®] Quadrivalent and Adults \geq 65 Years of Age Who Received Fluzone[®] High-Dose Quadrivalent, Influenza Vaccines, 2021–2022 Formulations

Brief Title:

Annual Study for Collection of Serum Samples in Children and Older Adults Receiving the 2021–2022 Formulations of Fluzone Quadrivalent Vaccine and Fluzone High-Dose Quadrivalent Vaccine, Respectively

Rationale:

The aim of Study GRC00102 is to obtain serum samples for submission to the Center for Biologics Evaluation and Research (CBER) to aid in the influenza vaccine strain selection process. Children 6 months to < 9 years of age will receive the 2021–2022 formulation of Fluzone Quadrivalent vaccine and adults \geq 65 years of age will receive the 2021–2022 formulation of Fluzone High-Dose Quadrivalent vaccine.

No early safety data review is planned for this study.

Objectives and Endpoints:

Objectives	Endpoints			
Primary				
 To provide serum samples (collected from participants before vaccination [Blood Sample 1] and after final vaccination [Blood Sample 2]) to CBER for further analysis by the World Health Organization (WHO), Centers for Disease Control and Prevention (CDC), and Food and Drug Administration (FDA) to support formulation recommendations for subsequent influenza vaccines. In addition, serum samples from adult participants may be further analyzed by the Sponsor to assess breadth of immune response induced by the study vaccines. 	There are no endpoints for this objective.			

Overall Design

Type of design	Parallel, multi-site
Phase	IV
Control method	None
Study population	Children 6 months to < 9 years of age
	Adults ≥ 65 years of age
Countries	United States
Level and method of blinding	None (open-label)
Study intervention assignment method	Participants will not be randomized

Brief Summary:

This is a phase IV, multi-site, open-label study. The study will collect serum samples from children 6 months to < 9 years of age who received Fluzone Quadrivalent vaccine and adults ≥ 65 years of age who received Fluzone High-Dose Quadrivalent vaccine for submission to CBER to aid in the influenza vaccine strain selection process.

Study Duration:

Participants 6 months to < 9 years of age: 28 (window, 28–35) days following the last dose of influenza vaccine, including serious adverse event (SAE)/adverse event of special interest (AESI) follow-up).

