2.1 Study Rationale

The aim of Study GRC00102 is to obtain serum samples for submission to CBER to aid in the influenza vaccine strain selection process. Children 6 months to < 9 years of age will receive the 2021–2022 formulation of Fluzone Quadrivalent vaccine and adults \geq 65 years of age will receive the 2021–2022 formulation of Fluzone High-Dose Quadrivalent vaccine.

Serum samples from participants will be supplied to CBER after the completion of this study (i.e., after the last participant completes the last study visit). In turn, CBER will distribute the serum samples to the CDC and other WHO-collaborating laboratories for evaluation against circulating influenza viral strains. It is expected that the immunologic and surveillance data will be presented at WHO meetings where the vaccine strain selections will be made for the Southern and Northern hemispheres and at the FDA Vaccines and Related Biological Products Advisory Committee meeting for selection of strains for influenza vaccines, including those to be distributed in the United States.

No early safety data review is planned for this study.

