Vaccination with influenza vaccine is the primary method for preventing influenza and its severe complications. It has been shown to be effective in reducing influenza-associated morbidity and mortality in groups at increased risk for influenza-related complications such as infants and young children and persons 50 years of age and older. Of note, immune responses to the vaccine are lower in seniors than those in young healthy adults (5). Strategies to improve immune responses to the vaccine in the elderly population could provide substantial additional reductions in influenza-associated morbidity and mortality. One approach is to increase the dose of HA in inactivated vaccines. Previous studies evaluating the immune responses in terms of hemagglutination inhibition (HAI) antibodies with higher doses of HA per strain in different influenza vaccines support a dose-response effect (6).

Fluzone High-Dose Quadrivalent vaccine contains 60 µg HA per virus strain per dose, which is 4 times the amount of HA per strain per dose in Fluzone Quadrivalent vaccine. It was developed for use in the elderly to elicit enhanced immune responses against influenza through the use of

higher antigen content, with the goal of providing older adults with improved protection against the disease.

During this study, Fluzone Quadrivalent or Fluzone-High-Dose Quadrivalent vaccine will be administered according to the guidelines in the Prescribing Information and only to persons for whom the respective vaccine is indicated.

The objective of this study is to provide serum samples collected from children 6 months to < 9 years of age who receive Fluzone Quadrivalent vaccine and adults ≥ 65 years of age who receive Fluzone High-Dose Quadrivalent vaccine to CBER. The serum samples are used for further analysis by the WHO, CDC, and FDA to support formulation recommendations for subsequent influenza vaccines. In addition, serum samples from adult participants may be further analyzed by the Sponsor to assess breadth of immune response induced by the study vaccines.

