6.8 Concomitant Therapy

Reportable medications include medications that may affect the interpretation of safety data or may interfere with the development or measurement of the immune response (e.g., the use of immune-suppressors, immune-modulators, or some antibiotics that can affect certain bioassays). Some medications such as steroids can affect both the evaluation of the safety and the immune response to a vaccine.

This may include medications of interest that were started prior to the day of vaccination, and even stopped prior to enrollment if there is a reasonable possibility that they may have an impact on safety and / or immune assessment during study participation.

The following reportable medications are defined:

- Category 2: medications impacting or that may have an impact on the immune response (eg, other vaccines, blood products, antibiotic classes that may interfere with bioassays used by Sanofi Pasteur laboratory or other testing laboratories, systemic steroids/corticosteroids, immune-suppressors, immune-modulators with immunosuppressive properties, anti-proliferative drugs such as DNA synthesis inhibitors
- Category 3: medications impacting or that may have an impact on both the safety and the immune response (eg, systemic steroids/corticosteroids)

Reportable medications will be collected in the CRF from the day of each vaccination to the end of the follow-up period (i.e., from Visit 1 through Visit 2 for participants receiving 1 dose of study vaccine or from Visit 1 through Visit 3 for participants receiving 2 doses of study vaccine).

Dosage and administration route, homeopathic medication, topical and inhaled steroids, as well as topical, ophthalmic, and ear treatments will not be recorded.

Topical analgesics should not be applied at the site of vaccination; however, if they are applied inadvertently to the vaccination site, they should be recorded as a Category 3 medication.

Medications given in response to an AE will be captured in the "Action Taken" section of the AE CRF only. No details will be recorded in the concomitant medication Form of the CRF unless the medication(s) received belongs to one of the pre-listed categories. Medications will not be coded.

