7.1.2 Definitive Contraindications

Participants will permanently discontinue (definitive discontinuation) study intervention for the reasons listed below. These participants must not receive any additional dose of study intervention but should continue to be followed for safety. Additional unscheduled visits may be performed for safety reasons and information will be reported in the source documents.

Should a participant experience at least one of the conditions listed below, the Investigator will discontinue vaccination:

- DCI01: An anaphylactic or other significant allergic reaction to the previous dose of vaccine
- DCI02: Receipt of any non-study vaccine (including a non-study dose of 2021–2022 influenza vaccine), blood-derived immune globulins, blood, or blood-derived products between Visit 1 and Visit 2.
- DCI03: Bleeding disorder, receipt of anticoagulants, or thrombocytopenia, which may be a contraindication for IM vaccination, at the discretion of the Investigator.
- DCI04: Development of any condition that in the opinion of the Investigator would pose a health risk to the participant or could interfere with the evaluation of the study vaccine

(including GBS, clinically significant developmental delay, neurologic disorder, seizure disorder, human immunodeficiency virus infection, hepatitis B, or hepatitis C).

- DCI05: Development of immunodeficiency; or receipt of immunosuppressive therapy such as anti-cancer chemotherapy or radiation therapy; or receipt of long-term systemic corticosteroid therapy (prednisone or equivalent for more than 2 consecutive weeks).
- DCI06: Adverse events that are considered a contraindication for further participation in the study.

In the event of a local or national immunization program with a COVID-19 Vaccine, participants who receive the vaccine mentioned above at any time during the study will not be withdrawn from the study.

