8.9 Leftover Biological Samples and Use of Data

Any unused part of the biological samples collected for this study (serum samples) are being retained in long-term storage to support answers to regulatory questions related to the product's licensure and the potential revalidation of the study results.

In addition, participants or participants' parents/legally acceptable representatives will be asked to indicate in the ICF whether they will permit the future use of any unused stored biological samples for other tests, unless prohibited by local laws or IRBs/IECs (in such case, consent for future use of any unused biological samples will not be included in the site-specific ICF). If they refuse permission, the biological samples will not be used for any testing other than that directly related to this study. If they agree to this future use, they will not be paid for giving permission. The aim of any possible future research is unknown today, and may not be related to this particular study. It may be to improve the knowledge of vaccines and their mechanism of action, the knowledge of infectious diseases, or to improve existing tests or develop new tests to assess vaccines, or to help identify new vaccine targets or biomarkers that predict participant response to the vaccine. Such research may also include, but is not limited to, performing assessments on DNA, RNA, proteins or metabolites. If future research on genetic material is performed, a specific individual consent will be obtained.

Data and samples will be used in compliance with the information provided to participants in the ICF Part 2 (future research). In the event future research is conducted for other purposes, the study participants will be informed of those purposes and will be given means to object to the use of their biological samples or data for those research projects.

All study participant data and biological samples will be coded such that no direct identifiers will be linked to participants. Coded data and biological samples may be transferred to a Sponsor site (or a subcontractor site), which may be located outside of the country where the study is conducted. The Sponsor adopts safeguards for protecting participant confidentiality and personal data (see Section 10.1.4).

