9.4.1 General Considerations

Summaries of baseline demographic characteristics of the study participants will be presented. The number of participants enrolled and their age at enrollment (mean, median, and minimum and maximum), sex, race, and ethnic origin will be summarized, along with the number and description of protocol deviations. Listings of participants by age group, sex, vaccine received, and history of vaccination in the previous seasons will be provided.

9.4.2 **Primary Endpoint(s)**

There are no primary endpoints for this study.

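### Does the protocol leave open whether sponsor breadth testing of adult sera belongs to the study, and must Section 9.4 count the sera?

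*Combined protocol and SAP*

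**What the plan says.** The objective, given in the Synopsis (Section 1.1) and in Table 3.1, is to supply sera taken before vaccination and after the final vaccination to CBER, for later analysis by WHO, CDC and FDA. The same table cell adds that "serum samples from adult participants may be further analyzed by the Sponsor to assess breadth of immune response induced by the study vaccines", and Section 2.2 repeats this beside the study objective. The cell states that the objective has no endpoints.

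Section 8.1.2 says "No immunogenicity data will be obtained in the study", and Section 8.7 only refers back to it. Section 8.9, on leftover samples, asks participants whether unused stored samples may be used for other tests. It then says: "If they refuse permission, the biological samples will not be used for any testing other than that directly related to this study".

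No separate SAP will be written, so Section 9.4 is the whole analysis specification. It covers enrollment, demographics, protocol deviations and SAEs/AESIs, and says "Listings of participants by age group, sex, vaccine received, and history of vaccination in the previous seasons will be provided". It mentions neither serum counts nor medications. Section 6.8 collects Category 2 medications, defined as "medications impacting or that may have an impact on the immune response", and Category 3 medications, which may affect both safety and immune response. On COVID-19 vaccination, Section 7.1.2 says "participants who receive the vaccine mentioned above at any time during the study will not be withdrawn from the study".

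**The concern.** Two things look wrong on a first reading.

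The first is the status of the sponsor's breadth testing. Its place under the primary objective suggests study testing. Section 8.1.2 suggests that it lies elsewhere. No sentence connects the two. If that status decided what Section 8.9 allows, an adult who refused future use could be included by a reader of Section 3 and excluded by a reader of Section 8.1.2. A sample might then be used beyond the permission given, or the testing might be restricted to adults who opted in, a limit the objective does not mention.

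The second is reporting. Supplying paired sera is the study's one deliverable, yet the planned output does not show how many pairs were obtained or which came from participants exposed to another vaccine or a blood product. Because COVID-19 vaccine recipients stay in the study, such sera can occur.

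**Working it through.** **Planned numbers.** The Synopsis gives three groups of 30, and 30 + 30 + 30 = 90, the stated total. With two samples each, 2 × 90 = 180 sera are planned, of which 2 × 30 = 60 are adult (30 pairs). Adult volume is 2 × 20 mL = 40 mL and child volume is 2 × 5 mL = 10 mL, matching the limits in Section 8. No power, margin or target number of pairs is stated, so there is no sample-size figure to reproduce.

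**How many adults could be affected.** The documents give no refusal rate, so r is assumed. Expected refusers = 30r. Chance of at least one = 1 − (1 − r)^30.

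| Assumed r | Expected refusers | Chance of at least one | Expected adult pairs if refusers are excluded, 30(1 − r) |
|---|---|---|---|
| 2% | 0.6 | 1 − 0.98^30 = 45% | 29.4 |
| 5% | 1.5 | 1 − 0.95^30 = 79% | 28.5 |
| 10% | 3.0 | 1 − 0.90^30 = 96% | 27 |
| 20% | 6.0 | 1 − 0.80^30 = 99.9% | 24 |

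These figures matter only if the optional testing takes place and if Section 8.9 really does shut refusers out.

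**Does Section 8.9 shut them out?** The passages, side by side:

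1. Section 8.1.2 concerns what data the study itself will obtain. Section 8.9 concerns whether a test relates directly to the study. These are different questions, and a no to the first does not imply a no to the second.
2. Section 8.9 seeks permission for other tests on unused stored samples. A use written into the primary objective is not naturally one of those other tests.
3. Apply the worrying reading to the public laboratories. Section 2.1 says "Serum samples from participants will be supplied to CBER after the completion of this study", and the resulting immunologic data come later still. Those data are no more obtained in the study than the sponsor's would be. If Section 8.1.2 governed permission, a refuser's serum could not be assayed for strain selection either, in any of the three groups, which would defeat the study's purpose. A reading with that result cannot be the intended one.
4. Both uses are described as further analysis of sera the study has delivered. On that footing Section 8.1.2 is accurate: the study collects and hands over sera and builds no immunogenicity dataset. Section 9.4 then owes no output for an optional later assay with no endpoint.

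**Serum counts and medications.** The schedules of activities (Tables 1.2 and 1.3) mark both blood sampling and reportable medications for collection in the CRF. Counts of first samples, second samples and pairs, and flags for Category 2 or 3 exposure, can therefore be produced without new data. Section 9.4.1 already reports protocol deviations, where missed draws could appear. Exclusion criteria E13 and E15 reduce the chance of exposure to other vaccines or blood products, and DCI02 stops further vaccination in two-dose children who receive them between Visits 1 and 2.

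**The case for a change.** The strongest case for a change is that permission to use human samples should not depend on inference. Section 8.1.2 is unqualified, Section 8.9 does not name breadth testing, and its stated reasons for retaining samples (licensure questions and revalidation of results) do not obviously cover it. That the testing is optional does not help, because an optional assay still needs a clear permission base. Nor does timing, since the supply to CBER also follows the last visit. One sentence would settle the matter. On reporting, a study whose only product is paired sera would reasonably state how many pairs it produced.

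What stands is that the passages are not cross-referenced, and that Section 9.4 contains no serum count or medication output. What does not stand is the step from a missing cross-reference to two equally available answers. The point about timing works against the concern: it shows that post-study use can be central to the study. The consent pages are not in the review copy, and Section 8.9 refers to a part of the consent form devoted to future research, so a mismatch with the permission given is conjecture. A serum table would be a sensible courtesy to readers, but its absence is a reporting preference and not an error.

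**Conclusion.** No change is needed. The difference between the primary objective and Section 8.1.2 is a gap in wording that closes when the sections are read together: the sponsor's breadth testing, like the public laboratories' work, is later use of sera for a stated purpose of the study. The missing serum and medication tabulations are a gap that analysts can fill from the CRF.

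The expected 0.6 to 6.0 adults out of 30 rests on assumed refusal rates of 2% to 20%, and is an upper limit on reach, not a count of anyone wrongly tested or excluded. The study has no endpoint, hypothesis, power calculation or required number of pairs, so following the plan as written still delivers the sera and alters no result. No consent breach or shortfall is shown. The conclusion assumes that the consent form, which could not be checked, does not itself restrict sponsor testing to participants who agreed to future use.
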